The power calculation above is for a smaller effect size than the Noar 2016 paper, $d=0.25$. If we enroll 253 per group, we will have 80% power to detect a small difference between the optimal and sub-optimal group.

For our purposes, that would mean enrolling a total of at least 759 people.

How does this compare to [name]'s simulations?

Based on [name]'s simulations, if we use 3 time points, and enroll around 750 people, we should be able to see an effect size of 0.35. This simulation is also very dependent on the assumptions that we started with.

Recommendation:

To be even more conservative, I would like to enroll at least 800 participants into our study to have enough power to see a $d=0.25$ difference between the optimal and sub-optimal groups.

Framework

Superiority – standard hypothesis testing framework

Statistical Interim Analyses and Stopping Guidance

NA, this study is no more than minimal risk to participants and does not pose a risk to their health, so we did not carry out any interim analyses or set guidelines for stopping the trial early.

Timing of Final Analysis

Final analysis will take place after all data collection for the RCT is complete.

Timing of Outcome Assessments

Time	Pre-Test	Morning	Post-Test 1	Post-Test 2

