Gay, lesbian, or bisexual								
Current Cigarette Smoking								
Current smoker								
Nonsmoker								
Fagerstrom Nicotine Dependence Score (FTND)								
Trust in FDA								
Number of Times Participants Viewed a Message During Follow Up								

To update Table 1 see 'Table 1 V1.xlsx' in Analysis Plan folder

Analysis

Outcome definitions

- Quit intentions [Time Frame: day 16] PRIMARY OUTCOME
 - 3 item measure with high reliability, average of the 3 items to create a score range 1-4 (Brewer et al., 2016, 2018; Klein, Zajac, & Monin, 2009)
 - We will compare the differences between pre and post
- Number of cigarettes smoked each day [Time Frame: Measured daily on days 1-15]
 - Continuous, Modified from FTND (Heatherton, Kozlowski, Frecker, & Fagerström, 1991; Storr, Reboussin, & Anthony, 2005)
- Number of cigarettes forgone each day [Time Frame: Measured daily on days 1-15]
 - Continuous, adapted from Brewer 2016 (Brewer et al., 2016)
 - May be zero inflated, if yes, may choose to dichotomize to 0/1
- Number of cigarettes butted out each day [Time Frame: Measured daily on days 1-15]
 - Continuous, adapted from Brewer 2016 (Brewer et al., 2016)
 - May be zero inflated, if yes, may choose to dichotomize to 0/1
- Quit attempts during the study [Time Frame: Measured on days 16 and 32]
 - Adaptation from Fagan (Fagan et al., 2007)
 - May be zero inflated, if yes, may choose to dichotomize to 0/1
- Awareness of quitline [Time Frame: Measured on day 16]
- Recall of quitline phone number [Time Frame: Measured on day 16]
- Use of the quitline during the study [Time Frame: Measured on days 16 and 32]
- Intention to use the quitline [Time Frame: Measured on days 16 and 32]
- Quit intentions [Time Frame: Measured on day 32]
 - 3 item measure with high reliability, average of the 3 items to create a score range 1-4 (Brewer et al., 2016, 2018; Klein et al., 2009)
 - We will compare the differences between pre and post
- Self Efficacy [Time Frame: Measured on days 16 and 32]

- 1 item (“IARC HANDBOOKS OF CANCER PREVENTION,” n.d.; Thrasher, Swayampakala, Borland, et al., 2016; Thrasher, Swayampakala, Cummings, et al., 2016)
- Response Efficacy [Time Frame: Measured on days 16 and 32]
 - 1 item (Thrasher, Swayampakala, Cummings, et al., 2016)

Analysis Methods

Analysis methods will depend on the time point that the outcome was measured. Post test measures will be analyzed differently than measures from the daily surveys, as outlined below.

Post test measures

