What analysis method will be used and how treatment effects will be presented

Linear regression for continuous outcomes, logistic for dichotomous.

Any adjustment for covariates

Covariates included for the imputation (in addition to treatment group):

- Dose of ads (# of times participants viewed a message)
- Gender (Male, Female, Other) (The GenIUSS Group, 2014)
- Age (continuous)
- Poverty Status (Above or Below Poverty Line)(Brewer et al., 2018; Department of Health and Human Services, 2017)
- Education (6 categories, same as phone survey)
- FTND Sum Using scoring from Heatherton et al. 1991 (Fagerstrom Test for Nicotine Dependence)(Fagerstrom, Heatherton, & Kozlowski, 1990; Heatherton et al., 1991)

Covariates included in the analysis model (in addition to treatment group):

- Dose of ads (# of times participants viewed a message)

Methods used for assumptions to be checked for statistical methods

For continuous outcomes, we assume the distribution of dependent variable given a predictor variable (intervention) is 1) independent 2) normality 3) constant variance (homogeneity of variance). We can check normality with Q-Q plot of the residual or perform Wilk-Shapiro test and use a scatter plot of residual on predictor variable (intervention) to check independence and constant variance.

Details of alternative methods to be used if distributional assumptions do not hold (eg normality, proportional hazards, etc)

If we have a violation for normality assumption, we can have two options: 1) transform our data so that the shape of our response variable become normally distributed or 2) choose the non-parametric method like Kruskal-Wallis which does not require the assumption of normality. The ANOVA can be considered a robust test against the normality assumption though. If the assumption of homogeneity of variances has been violated, we can use Welch or Brown and Forsythe test. Even though we alternatively perform a Kruskal-Wallis test, in most cases, Welch test is best. We don't expect to have dependency issues in our data.

Any planned sensitivity analyses for each outcome where applicable

Sensitivity analyses may be carried out using a 'complete case analysis' framework

Any planned subgroup analyses for each outcome including how subgroups are defined

None a priori

Missing Data

Multiple imputation will be used so that everyone who was randomized to an intervention will be included in the primary analysis

Additional Analyses

None a priori

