Nicotine Dependence ⁷	How many cigarettes per day do you smoke?	0 = 10 or less 1 = 11-20 2 = 21-30 3 = 31 or more	FTND4_Pre	FTND4_Post1	FTND4_Post2
	Do you smoke more frequently during the first hours after waking than during the rest of the day?	1 = Yes 0 = No	FTND5_Pre	FTND5_Post1	FTND5_Post2
	Do you smoke if you are so ill that you are in bed most of the day?	1 = Yes 0 = No	FTND6_Pre	FTND6_Post1	FTND6_Post2
Page Break					
Previous Quit Attempts ⁸	How many times during the past 12 months have you stopped smoking for 1 day or longer because you were trying to quit smoking?	Dropdown (0-365)	PQA_Pre		
Quit Attempts ⁸	Since you started this study, how many times have you stopped smoking for 1 day or longer because you were trying to quit smoking?			QuitAtt_Post1 Dropdown 0-16	QuitAtt_Post2 Dropdown 0-32
Smoking Status ⁹	Do you now smoke cigarettes every day, some days or not at all?	2=Every day 1=Some days 0=Not at all	Smoke_Stat_Pre	Smoke_stat_pos t1	Smoke_Stat_post 2
Page Break					

Construct (Source)	Question Text	Response Option	Pretest Var Name	Post 1 Var Name	Post 2 Var Name
Quit Line Awareness	Do you know what national phone number you can call for help to quit smoking?	1 = Yes 0 = No (If no, skip the next question)		QLAware1	
Page Break					
Quit Line Awareness follow up	What is the national phone number?	Text Box		QLAware2	
Page Break					
Quitline Use	Since you started this study, have you called the Quitline (national phone number for help to quit smoking)?	1 = Yes 0 = No		QL_Use_Post1	QL_Use_Post2
Page Break					
Quit Intention ^{4,10}	How interested are you in quitting smoking in the next month?	4=Very interested 3=Somewhat interested 2=A little interested 1=Not at all interested	QI1_Pre	QI1_Post1	QI1_Post2
	How much do you plan to quit smoking in the next month?	4=Very much 3=Somewhat 2=A little 1=Not at all	QI2_Pre	QI2_Post1	QI2_Post2
	How likely are you to quit smoking in the next month?	4=Very likely 3=Somewhat likely 2=A little likely 1=Not at all likely	QI3_Pre	QI3_Post1	QI3_Post2
PAGE BREAK					
Quitline Intention	If you were to quit smoking in the next month, how likely are you to call the national quitline for help?		QLI_Pre	QLI_Post1	QLI_Post2
Littering Intention ⁴	How likely are you to dispose of your cigarette butts by dropping them on the ground in the next month?		LI_Pre	LI_Post1	LI_Post2
Page Break					

Construct (Source)	Question Text	Response Option	Pretest Var Name	Post 1 Var Name	Post 2 Var Name

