Self Efficacy ¹¹⁻¹³	If you decided to give up smoking completely in the next month, how sure are you that you would succeed?	5=Extremely 4=Very much 3=Moderately	SE_Pre	SE_Post1	SE_Post2
Response Efficacy ¹¹	How much do you think you would benefit from health and other gains if you were to quit smoking permanently in the next month?	2=A little 1=Not at all	RE_Pre	RE_Post1	RE_Post2
PAGE BREAK					
Positive Thoughts ^{14,15}	During the past 24 hours, how often did positive thoughts about smoking come to mind (thoughts that just popped into your head, or you caught yourself thinking)?	5=All of the time 4=Often 3=Sometimes 2=Rarely 1=Never	Freq_Pos_Pre	Freq_Pos_Post1	Freq_Pos_Post2
PAGE BREAK					
Positive Thoughts ^{14,15}	[displayed if freq_pos ne never] Considering only your positive thoughts about smoking during the past 24 hours, how positive were these thoughts?	1=Not at all Positive 2=Slightly Positive 3=Moderately Positive 4=Very Positive 5=Extremely Positive	Degree_Pos_Pre	Degree_Pos_Post1	Degree_Pos_Post2
PAGE BREAK					
Negative Thoughts ^{14,15}	During the past 24 hours, how often did negative thoughts about smoking come to mind (thoughts that just popped into your head, or you caught yourself thinking)?	5=All of the time 4=Often 3=Sometimes 2=Rarely 1=Never	Freq_Neg_Pre	Freq_Neg_Post1	Freq_Neg_Post2
PAGE BREAK					
Negative Thoughts ^{14,15}	[displayed if freq_neg ne never] Considering only your negative thoughts about smoking during the past 24 hours, how negative were these thoughts?	1=Not at all Negative 2=Slightly Negative 3=Moderately Negative 4=Very Negative 5=Extremely Negative	Degree_Neg_Pre	Degree_Neg_Post1	Degree_Neg_Post2
Page Break					

Construct (Source)	Question Text	Response Option	Pretest Var Name	Post 1 Var Name	Post 2 Var Name
Current OTP Use ¹⁶	In the past 30 days, which of the following products have you used at least once? (Pick all that apply)	
 1. Cigars, cigarillos, or little cigars 2. Smokeless tobacco, for example chewing tobacco, snuff, dip, or snus 3. Electronic cigarettes, e-cigarettes, or other vaping devices 4. Water pipes or Hookah 5. Clove cigarettes 6. Roll your own cigarettes 7. None of the above [exclusive] 	OTPUse_Pre1, OTPUse_Pre2, OTPUse_Pre3, OTPUse_Pre4, OTPUse_Pre5, OTPUse_Pre6, OTPUse_Pre7		

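### Self-efficacy and response efficacy are modelled at days 16 and 32 without their own pre-test scores, which are collected; adding them would gain precision at almost no cost

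*Combined protocol and SAP*

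**What the plan says.** The SAP gives one rule for every post-test measure (Analysis Methods, Post test measures): "Linear regression for continuous outcomes, logistic for dichotomous". Beside treatment group, the analysis model has one covariate, dose of ads. The imputation list adds gender, age, poverty status, education and the FTND sum, but no pre-test score of any outcome.

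Under Outcome definitions, quit intentions at day 16 and at day 32 each carry a line specifying a pre/post comparison. The entries "Self Efficacy [Time Frame: Measured on days 16 and 32" and "Intention to use the quitline [Time Frame: Measured on days 16 and 32" carry no such line, and neither does response efficacy.

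On what is collected at pre-test:

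- **Self-efficacy and response efficacy.** Both are in the pre-test column of Timing of Outcome Assessments and of Constructs by Timeframe in Appendix A. The Appendix A item table gives SE_Pre and RE_Pre with the same question at all three waves; the self-efficacy item reads "If you decided to give up smoking completely in the next month, how sure are you that you would succeed".
- **Intention to use the quitline.** The item table names QLI_Pre for the question "If you were to quit smoking in the next month, how likely are you to call the national quitline for help". Both construct tables list this measure at the two post-tests only.

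**The concern.** When the same item has been asked before randomisation, the participant's own earlier answer is usually the best available predictor of the later one. Putting it in the model removes that part of the residual variance and narrows the interval for the arm contrast. Here the plan collects the baseline and then does not use it.

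The contrast concerned is optimal versus sub-optimal, which Sample Size expects to show the smallest effect. The same section describes the optimal messages as adding quitline and self-efficacy information, so self-efficacy is a natural place to look for an effect of that content. What is at stake is the width of the intervals, and hence the power, for secondary outcomes.

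**Working it through.** **Inputs from the documents**

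- Significance level 0.05 (Confidence Intervals and P Values). Sidedness is not stated; Framework says only "standard hypothesis testing framework".
- Sizing: "If we enroll 253 per group, we will have 80% power to detect a small difference between the optimal and sub-optimal group", by a two-sample t-test at one time point.
- Effect size: the target of 800 is chosen "to have enough power to see a $d=0.25$ difference between the optimal and sub-optimal groups". This is set for quit intentions.
- Equal allocation; 800/3 is about 266 per arm.

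**Assumptions, because the documents are silent**

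- d = 0.25 is carried over to the secondary outcomes, then varied from 0.10 to 0.40.
- The pre-post correlation ρ is varied from 0.3 to 0.7.
- The five-point items are treated as continuous, and the dose term is set aside.

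**Step 1: reproduce the plan's figure.** n per arm = 2(1.96 + 0.842)²/0.25² = 251.2, so 252. The noncentral t gives 252.1, rounded up to 253; 3 × 253 = 759, as stated. A one-sided test would need 198 per arm, so the plan's figure is two-sided.

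**Step 2: effect of adjustment.** With the own baseline as a covariate, the residual SD is multiplied by √(1 − ρ²). The noncentrality is d√(n/2)/√(1 − ρ²).

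For n = 253 and d = 0.25, the unadjusted value is 0.25 × √126.5 = 2.81, which gives power of 80.1%. At ρ = 0.5 it is 2.81/0.866 = 3.25, which gives 90.0%.

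| ρ | Power, 253 per arm | Gain (points) | Power, 266 per arm | Gain (points) |
|---|---|---|---|---|
| no baseline | 80.1% | – | 82.1% | – |
| 0.3 | 83.7% | 3.6 | 85.5% | 3.4 |
| 0.4 | 86.5% | 6.3 | 88.1% | 6.0 |
| 0.5 | 90.0% | 9.8 | 91.4% | 9.3 |
| 0.6 | 93.9% | 13.8 | 94.9% | 12.9 |
| 0.7 | 97.6% | 17.4 | 98.1% | 16.0 |

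Gains are taken before rounding. At ρ = 0.5 the residual variance falls by 25%, the interval narrows by 1 − √0.75 = 13%, and the n per arm for 80% power falls from 252 to 189.

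**Step 3: vary the effect size** (ρ = 0.5, 253 per arm).

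| d | 0.10 | 0.15 | 0.20 | 0.25 | 0.30 | 0.35 | 0.40 |
|---|---|---|---|---|---|---|---|
| Gain (points) | 5.2 | 10.2 | 12.4 | 9.8 | 5.3 | 1.9 | 0.5 |

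**Step 4: smaller analysed numbers.** Analysis Populations allows complete-case analysis of secondary outcomes. If 80% of 266 per arm were analysed (an assumption; about 213), power at d = 0.25 and ρ = 0.5 would go from 73.0% to 84.4%, a gain of 11.4 points.

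**Step 5: is a change score an alternative?** Its variance is 2(1 − ρ) times that of the post-test score. At ρ = 0.5 the factor is 1, so power is 80.3% either way (normal approximation). At ρ = 0.3 the change score is worse, at 66.2%. The gain comes from using the baseline as a covariate.

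**The case against.** The best defence is that the trial is not sized on these outcomes and the plan is valid without the baseline. Under randomisation the unadjusted contrast is unbiased. Any chance imbalance at baseline is part of the sampling error that the interval already covers. All of this stands. A reader might infer that leaving out the pre-test score biases the comparison, but the documents do not support that.

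Three other readings go too far:

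- **That about 10 points of power are lost.** This is one cell of the tables above. It needs both ρ = 0.5 and d = 0.25, and the documents give neither for these outcomes. Nor do they support arguing for a high ρ because the items are single questions on short scales: single items tend to carry more measurement error, which lowers ρ. The correlation may also differ between day 16 and day 32.
- **That all three baselines are in hand.** For quitline intention the item table and the two construct tables conflict, so availability is not established.
- **That quit intentions is better served by its pre/post comparison.** If that means a change score, Step 5 shows no advantage at ρ = 0.5 and a loss below it.

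It is also fair to object that the SAP does not label these items as continuous and allows transformation or Kruskal-Wallis. The power figures apply only if linear regression is used.

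None of this is a reason to leave out a pre-test score that has been collected.

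**Conclusion.** The point holds as an optional improvement in efficiency for self-efficacy and response efficacy. Their pre-test items are collected, and no stated model uses them.

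If the outcomes are analysed as continuous with 253 per arm and d = 0.25, the gain in power is 3.6 to 17.4 points for ρ from 0.3 to 0.7. At ρ = 0.5 it is 0.5 to 12.4 points for d from 0.10 to 0.40. Both d and ρ are assumptions for these outcomes, so the gain should be quoted as a range. Validity is not in question.

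For intention to use the quitline, the point is conditional on the pre-test item having been fielded.

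**What to change.** 1. In Analysis Methods, Post test measures, add SE_Pre to the self-efficacy models and RE_Pre to the response-efficacy models, at day 16 and at day 32. State that these items are analysed as continuous, if that is the intention.
2. If these outcomes are imputed, add the same pre-test scores to the imputation model.
3. Reconcile the Appendix A item table, which names QLI_Pre, with the pre-test columns of Timing of Outcome Assessments and Constructs by Timeframe, which omit quitline intention. Add QLI_Pre as a covariate in the same way only if the item was fielded; if it was not, correct the item table.
4. The SAP already names a final dataset, so date and record the change before arm comparisons are examined.

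The cost is SAP wording and one degree of freedom per model. No new data are needed.

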- *Cigarette littering message (Control)*: Messages about littering cigarettes will include text designed to discourage people from littering their cigarette butts, and an image related to the message. Each condition has 5 messages that will be repeated 3 times in a counterbalanced order. Study investigators used text developed by

investigators associated with our Center for Regulatory Research on Tobacco Communication. Design of these messages was developed by our team.

Randomization

At the end of the baseline survey, survey software will randomly assign participants to one of the three study arms. Participants will have an equal chance of being randomized to each study arm.

Sample Size

Sample Size Background:

Our study is examining the difference in quit intention for participants that receive 1) Optimal constituent messages with quitline information, and self-efficacy information, or 2) Sub-optimal constituent messages or 3) Messages about littering cigarette butts.

[figure not shown]
No studies from the literature that we could find examined difference in quit intention or quitting behaviors by optimal text vs. sub-optimal warning text vs. control in a warning or smoking communication context.

In a meta-analysis by Noar et al. 2014 (Pictorial cigarette pack warnings: a meta-analysis of experimental studies) the effect size between pictorial vs. text only warnings on intention to quit smoking was $d=0.54$. Other outcomes ranged between effect size $d=-0.03$ (recall of warning text), and $d=1.82$ (intention not to start smoking).

Assumptions for the power calculation:

- The smallest effect size between our groups will be between the optimal and sub-optimal group. If we can see a difference between these groups, we will be able to see the larger effects that we expect between the other groups.
- We will be using a continuous measure of quit intention (or treating quit intention as a continuous variable, and collecting it as a categorical response).
- The effect size on quit intention is likely to be smaller for added self efficacy and quit line text than for added pictorial images.
- To be conservative, we will use a one time measure to calculate power, repeated measures would add power to this analysis (decrease necessary sample size).
- We will use the d statistic to see what group size would have to be enrolled, and compare two means (optimal and sub-optimal) with a t-test

Based on these assumptions:

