Constructs	
 Sex, Sexuality Hispanic Origin, Race Address Education Age Health Household Size Income (above or below FPL) Trust in FDA and CDC Nicotine Dependence (FTND) Previous Quit Attempts Smoking Status Quit Intentions Littering Intention Self Efficacy Response Efficacy Positive and Negative Thoughts (Freq, Degree) Current OTP Use Knowledge of HE and Constituents Tripartite Risk Mental Health (K6) Study Information All Previous Day Behavior Qs 	
Previous day behaviors:
 
 Littering on the ground Littering from Car Forgoing Butting out Number of Cigarettes 
Cognitive Questions:
 
 Thinking about chemicals Thinking about risks Thinking about littering Thinking about quitting Message Negative Affect Message Credibility Perceived Effectiveness 	
 Nicotine Dependence (FTND) Quit Attempts Smoking Status Quitline Awareness Quitline Use Quit Intentions Quitline Intention Littering Intention Self Efficacy Response Efficacy Positive and Negative Thoughts (Freq, Degree) Current OTP Use Knowledge of HE and Constituents Tripartite Risk Credibility of FDA Mental Health (K6) Action Expectancies Reactance Talking about messages All Previous Day Behavior Qs Quality Assurance Questions 	
 Nicotine Dependence (FTND) Quit Attempts Smoking Status Quitline Use Quit Intentions Quitline Intention Littering Intention Self Efficacy Response Efficacy Positive and Negative Thoughts (Freq, Degree) Current OTP Use Knowledge of HE and Constituents Tripartite Risk Mental Health (K6) Action Expectancies All Previous Day Behavior Qs

Statistical Principles

Confidence Intervals and P Values

Level of statistical significance

$\alpha=0.05$

Description and rationale for any adjustment for multiplicity and, if so detailing how the type 1 error is to be controlled

NA

Confidence Intervals to be reported

95% CI

Adherence and Protocol Deviations

Definition of adherence to the intervention and how this is assessed including extent of exposure

Compliance with the protocol is assessed as follows:

- Completion of daily surveys, during which participants view intervention stimuli. % Compliance = number of daily surveys completed / 15 (number of surveys supposed to be completed)*100%
- Completion of post test surveys at post 1 and post 2

Description of how adherence to the intervention will be presented

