- Adherence for the daily surveys will be presented with completion % as well as the mean number complete by treatment group
- Completion of post test surveys will be presented by % completing each by treatment group

Definition of protocol deviations for the trial

- Minor protocol deviation: change in eligibility (ex: turning 66) between screening and baseline
- Minor protocol deviation: completing the wrong sequence of message days due to survey signal error
- Major protocol deviation: No protocol deviations in this trial will impact the safety or physical or mental integrity of the participants in the trial. A slightly older participant, or a participant that receives a slightly different number of messages will both be included as covariates during analysis, so they will not impact the scientific validity of the trial. Therefore, we do not classify any protocol deviations as 'major'

Description of which protocol deviations will be summarized

- Protocol deviations will not be summarized overall, but data related to the deviations will be included in manuscripts. For example, we will not say X participants were older than 65, but will include mean age in a demographic table by treatment group. Similarly, we will not include how many people completed an extra 'day' of the protocol, but we will report the mean number of days participants completed by treatment group.

Analysis Populations

Definition of analysis populations

Outcomes assessed only at post test (including quit intentions) will be analyzed using multiple imputation such that everyone who was randomized will be included in the analysis, and those with missing outcome data will have their outcomes imputed.

For outcomes that were measured daily, all participants that completed at least one of the daily surveys will be included in the planned repeated measure models.

Secondary outcomes may be analyzed using complete case analysis, without imputation.

Trial Population

Screening Data

Screening data will be provided based on the CONSORT guidelines, and CONSORT flow chart will be included with publications.

Eligibility

Minimum Age: 18 Years

Maximum Age: 65 Years

Sex: All

Gender Based: No

Inclusion Criteria:

[figure not shown]
- Have smoked at least 100 cigarettes in his or her lifetime
- Currently smoke cigarettes every day or some days
- Work or home access to the internet
- Email account that is regularly used
- Lives in the US
- Comfortable taking a survey in English

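### Pre-test quit intention is collected but is a covariate in neither the imputation nor the analysis model for the primary outcome, and the imputed quantity is not stated; every reading loses power against a baseline-adjusted analysis

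*Combined protocol and SAP*

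**What the plan says.** The SAP's outcome definitions name "Quit intentions [Time Frame: day 16] PRIMARY OUTCOME", scored as the mean of three items on a 1 to 4 scale, and add "We will compare the differences between pre and post". No model is written out beyond linear regression for continuous outcomes.

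The baseline value exists. The Pre-Test column under Timing of Outcome Assessments includes "Previous Quit Attempts Smoking Status Quit Intentions Littering Intention", and Appendix A gives each quit-intention item (the first is "How interested are you in quitting smoking in the next month") a pre-test variable, QI1_Pre to QI3_Pre.

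Under Analysis Methods, Post test measures, there are two covariate lists. The one headed "Covariates included for the imputation (in addition to treatment group" contains dose of ads, gender, age, poverty status, education and FTND sum. The analysis-model list contains dose of ads only.

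Analysis Populations says that "those with missing outcome data will have their outcomes imputed" but not whether the outcome is the day-16 score or the change. That section also groups quit intentions with outcomes measured only at post-test, which conflicts with the outcome definition and with Appendix A.

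The Sample Size section states "To be conservative, we will use a one time measure to calculate power, repeated measures would add power", sizes on a two-sample t-test at d = 0.25, and concludes "For our purposes, that would mean enrolling a total of at least 759 people". It then recommends at least 800.

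**The concern.** A baseline measurement on the outcome's own scale is usually the strongest predictor available, both for the outcome and for its missing values. Here it can enter only by subtraction, if the outcome is a change score, or not at all. Three things follow.

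- **Efficiency.** The primary contrast gives up precision that data already collected would supply.
- **Specification.** Two analysts following the SAP could impute different quantities and report different primary results.
- **Protection against selective dropout.** If day-16 missingness depended on baseline intention differently by arm, the variable that would correct for it is left out of the imputation.

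In addition, calling a one-time measure conservative is not generally true for an unadjusted change score.

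**Working it through.** **Inputs from the documents.** d = 0.25, alpha 0.05, 80% power, 253 per group, 759 in total, 800 planned (about 266 per arm), 1:1:1 allocation.

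**Assumed, because the documents give neither.** Pre-post correlation rho from 0.3 to 0.8; missing day-16 rate m of 10%, 20% or 30%, completely at random. Pre and post SDs are equal and set to 1, and d is in day-16 SD units. Dose is left out of all the models compared.

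**Step 1: reproduce the plan.** A two-sided two-sample t-test (noncentral t) at d = 0.25 needs 253 per group (power 80.1%), and 3 × 253 = 759. A one-sided test would need 198, so the plan is two-sided. At 266 per arm, power is 82.1%, or 82.2% by the normal approximation used below.

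**Step 2: complete data.** Relative variances V:

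- day-16 score, unadjusted: 1
- change score, unadjusted: 2(1 − rho)
- day-16 score adjusted for pre-test: 1 − rho²

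The adjusted variance is (1 − rho²) times the first and (1 + rho)/2 times the second. Both factors are below 1 whenever 0 < rho < 1. Power at 266 per arm:

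| rho | day-16 | change | adjusted |
|---|---|---|---|
| 0.3 | 82.2% | 68.3% | 85.6% |
| 0.5 | 82.2% | 82.2% | 91.5% |
| 0.7 | 82.2% | 96.1% | 98.1% |
| 0.8 | 82.2% | 99.5% | 99.8% |

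The change score beats a one-time measure only if 2(1 − rho) < 1, that is, rho > 0.5.

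**Step 3: missing outcomes.** With many imputations and Rubin's rules, V becomes:

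- (a) impute day-16 without pre-test, then subtract pre-test: true variance 1/(1 − m) + 1 − 2·rho; Rubin's estimate 2 − 2·rho(1 − m) + m/(1 − m)
- (b) impute the change: 2(1 − rho)/(1 − m)
- (c) impute and analyse day-16: 1/(1 − m)
- (d) pre-test in both models: (1 − rho²)/(1 − m)

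For (b) to (d), power is Φ(0.25/√(2V/266) − 1.96). At rho 0.5 and m = 0.2:

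- (b) V = 1.25, standard error 0.0970, power Φ(0.62) = 73.2%
- (d) V = 0.75/0.8 = 0.9375, standard error 0.0840, power Φ(1.02) = 84.6%
- (a) true variance 1.25 but Rubin's estimate 1.45, so the estimated variance is 1.16 times too large and power is 68.0%

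| rho, m = 20% | (a) | (b) | (c) | (d) |
|---|---|---|---|---|
| 0.3 | 58.5% | 58.7% | 73.2% | 77.1% |
| 0.5 | 68.0% | 73.2% | 73.2% | 84.6% |
| 0.7 | 80.7% | 91.5% | 73.2% | 95.1% |
| 0.8 | 88.1% | 98.3% | 73.2% | 99.0% |

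At rho 0.5, readings (a) to (c) run from 75.5–78.1% at 10% missing to 60.1–67.4% at 30%, against 88.5% and 79.5% for (d).

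A simulation with 20 imputations gave 66%, 72%, 73% and 84% for (a) to (d) at rho 0.5 and 20% missing. Adding a covariate standing in for FTND and demographics to the imputation (assumed correlation 0.3 with pre and post) gave 69%, 72%, 73% and 84%. Type I error under this missingness was 3–6% on every reading.

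**Step 4: an illustrative adverse case.** Let dropout log-odds change by 0.5 per SD of baseline, in opposite directions in two arms, with 20% missing. At rho 0.5 the false difference is −0.10 SD if day-16 is imputed and +0.10 SD if the change is imputed. Type I error is 14–18%, against 5% with pre-test in both models. At rho 0.7 the false differences are −0.14 and +0.06 SD and type I error is 12–29%, against 6%.

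**Step 5: margin for missing data.** 1 − 759/800 = 5.1%. At an assumed 20% missing, the one-time-measure target would need 759/0.8 ≈ 949.

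**The case against.** - **Pre-test may not be unused.** If the outcome is the change, pre-test enters through subtraction. This is right: the accurate statement is that it is not a covariate in either model. The change score remains less efficient, and the SAP does not settle that it is the outcome.
- **The loss can be trivial.** The same three items asked about 16 days apart could correlate highly. At rho 0.8 with the change imputed, power is 98.3% against 99.0%. This stands for that reading, but at the same rho the other two give 88.1% and 73.2%. The large losses need a low correlation, heavy missingness or an unfavourable reading, and neither parameter is in the documents.
- **The adverse case is constructed.** This stands. With the same dropout dependence in both arms the false difference is 0.00 and type I error 2–5%; with dependence in one arm only, type I error is 6–9%. Nothing in the documents suggests opposite-direction dropout, and FTND or dose in the imputation might recover part of the bias. The case shows that the unstated choice can matter; it does not predict that it will.
- **Dose is in both SAP models but not in these calculations.** This is true, so the power figures compare ways of handling baseline and are not forecasts for the exact SAP model.
- **Enrolling 800 gives some room.** It does, but only 5.1%, and no dropout rate is stated.

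**Conclusion.** The concern holds. The omission and the unstated imputation target are plain in the text, and the direction of the power loss needs only a pre-post correlation between 0 and 1 (with equal SDs). Its size is conditional on assumptions: about 9 points at rho 0.5 with complete data, and about 11 to 17 points with 20% missing. It shrinks to under 1 point at rho 0.8 if the change itself is imputed. If d = 0.25 is instead read in change-score SD units, then at 253 per arm the change score has 80.3% power and the adjusted analysis 93.7%, 90.1%, 86.2% and 84.2% at rho 0.3, 0.5, 0.7 and 0.8, so the direction is the same.

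With data missing completely at random, the planned contrast is unbiased and type I error is not inflated. This is chiefly a matter of efficiency and specification that should be fixed, not an invalid primary analysis.

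**What to change.** 1. State whether the day-16 score or the change is imputed, and correct the Analysis Populations wording that treats quit intentions as measured only at post-test.
2. Add pre-test quit intention to the imputation model.
3. Analyse the day-16 score by linear regression on arm with pre-test quit intention as a covariate, and treat the day-32 score the same way.
4. Restate power for that model under a stated correlation and retention rate, and drop or qualify the claim that the one-time measure is conservative.

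Optional: impute within arm, add daily predictors such as the thinking-about-quitting item, and use the same approach for self efficacy and response efficacy, which also have pre-test values.

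The cost is one dated SAP revision and one already-collected variable in each model. The SAP is dated July 24, 2018 and names a final dataset whose filename carries the previous day's date. The revision should therefore say whether arm comparisons had been seen. If they had, the adjusted result should be reported as a labelled sensitivity analysis. Restating power at that stage clarifies interpretation but cannot change enrolment.
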